4 STUDY PLAN

4.1 Study Design and Duration

This is a double-blind, randomized, multicenter, inpatient (and post-discharge outpatient) evaluation of the safety and efficacy of zavegeptant (BHV-3500) as compared to placebo in the treatment of COVID-19-associated pulmonary disease. The study drug will be zavegeptant or matching placebo, given as 10 mg IN dose every 8 hours (+/- 2 hours) for approximately 14 days (42 doses). The study will randomize approximately 120 subjects in a 2:1 ratio across the two treatment groups (zavegeptant or matching placebo). The randomization will be stratified by age (less than 60 years vs 60 years and older).

After signing informed consent and meeting eligibility criteria, the subject may be immediately randomized and dosed with the double-blind study medication (10 mg or matching placebo) and continue dosing every 8 hours (Q8h +/- 2 hours) up to approximately 14 days (42 doses).

[figure not shown]
For the purposes of this protocol, the start of Visit Day 1 will start when the 1st dose of study drug is administered until 24 hours later. Therefore, depending on the time when the 1st dose of study drug is administered, a visit day may spread over 2 calendar days. The last dose of study drug could be administered on Visit Day 14 but could actually occur on calendar day 15 of the study. The EOT or Day 15 assessments (depending on when subject stops study drug) should be completed after the last dose of study drug, and the subjects should remain in the hospital for a full 24 hours after their last dose of drug if they are to be released.

Randomization will be done through an IWRS that will be accessed by the unblinded research pharmacists or their designees. so that subjects can be dosed as soon as possible following consent and assessment of eligibility criteria. After completion of treatment, subjects will be followed out to Day 60 (+/- 15 days) during the post treatment phase.

This study has a duration approximately 8 weeks from time of Screening and obtaining consent through the Post-Dose Follow-up Visit (Day 60 +/- 15 days).

4.2 Study Schematic

Figure 2: BHV3500-203 Study Design

4.3 Schedule of Assessments

Table 1: Schedule of Assessments

Procedure	Screening Visit Day -2 to Day 1	Baseline Visit (Randomization) Day 1	Days 2 through 14 (+/- 1 day)¹	End of Treatment (EOT) Visit or Day 15 (+/- 1 day)²	Post-Treatment Phase Days 16 (+/- 1 day) through Day 29³ (+/- 2 days)	Day 60 (+/- 15 days)	Comments
Informed Consent	X						
Inclusion / Exclusion Eligibility Criteria	X	X					COVID-19 test should be positive by PCR test prior to study entry.

¹ If subjects are planned for release from the hospital prior to Day 15, they should discontinue drug for at least 24 hours and receive the End of Treatment assessments prior to discharge. They will be discontinued from study drug but continue in the study. All early discontinuations should be discussed with the Medical Monitor prior to planned release. Subjects will have follow-up phone calls on Days 15, 22, and 29 to assess 6-point ordinal scale, AEs/SAEs, and concomitant medications & procedures unless they are able to return for in-person visits. Subjects will need to return for at least 1 in-person visit on or before Day 60 to have the complete set of Day 29 assessments completed.

² EOT assessments should be completed after the last dose of study drug is administered and prior to hospital discharge. If the subject remains in the hospital and completes treatment (42 doses), Day 15 assessments are the same as EOT assessments. If the subject has EOT assessments completed prior to Day 15, then the Day 15 visit is a telephone visit.

³ After the Treatment Phase, if subjects remain in the hospital or are moved to a recovery facility, subjects should be evaluated daily for NEWS2, vitals, concomitant medications, AE/SAE, and SpO₂ and FiO₂ out to Day 29 with clinical labs collected per protocol on Days 22 and 29. Any clinical safety labs, urinalysis, LFTs, ECGs, or chest x-rays collected as per SOC should be entered into the eCRF in unscheduled visit pages for that assessment if not a per protocol assessment. If subjects are released from the hospital prior to Day 22, they should return for in-person visits on Day 22 (+/- 2 days) and Day 29 (+/- 2 days), if possible, and have a follow-up telephone visit at Day 60. If subjects are unable to return, then follow-up phone calls should be made on Days 22 (+/- 2 days) and 29 (+/- 2 days) to assess 6-point ordinal scale, AEs/SAEs, and concomitant medications and procedures. Subjects will need to return for at least 1 in-person visit on or before Day 60 to have the complete set of Day 29 in-person assessments completed.

Procedure	Screening Visit Day -2 to Day 1	Baseline Visit (Randomization) Day 1	Days 2 through 14 (+/- 1 day)¹	End of Treatment (EOT) Visit or Day 15 (+/- 1 day)²	Post-Treatment Phase Days 16 (+/- 1 day) through Day 29³ (+/- 2 days)	Day 60 (+/- 15 days)	Comments
Medical History	X						COVID-19 symptoms should be entered into medical history.
Physical Examination (PE)	X			X	X		Full Physical exam at screening and EOT. If a full PE is collected as per SOC within 48 hours prior to signing Informed Consent, this can be used as the Screening assessment. Directed PE on Day 29 (only).
Urinalysis (pH, specific gravity, ketones, nitrites, urobilinogen, leukocyte esterase, protein, glucose and blood)	X						Urinalysis will be collected per protocol at the Screening Visit. Urinalysis values collected within 48 hours of signing Informed Consent may be used as the Screening assessments. If urinalysis is collected as per SOC on any other days from Day 1 through Day 29 and clinically significant, these values should be entered into the eCRF on Unscheduled Visit Urinalysis pages.

Procedure	Screening Visit Day -2 to Day 1	Baseline Visit (Randomization) Day 1	Days 2 through 14 (+/- 1 day)¹	End of Treatment (EOT) Visit or Day 15 (+/- 1 day)²	Post-Treatment Phase Days 16 (+/- 1 day) through Day 29³ (+/- 2 days)	Day 60 (+/- 15 days)	Comments
Clinical Safety Laboratory Testing (Hematology: Hemoglobin, hematocrit, RBC count, WBC count with differentials, and platelets HbA1c Chemistry: Sodium, potassium, chloride, bicarbonate, calcium; glucose, BUN, serum creatinine, total protein, albumin, uric acid, LDH, and CK	X		X	X	X	X	Clinical safety labs collected within 48 hours of signing Informed Consent may be used as the Screening assessments. Clinical safety labs will be collected per protocol on Days 1, 2, 5, 10, 15, 22, and 29. If clinical safety labs are collected as per SOC on any other days and are clinically significant, these values should be entered into the eCRF on Unscheduled Visit Clinical Safety Labs pages. After hospital discharge, clinical safety labs should be done at in-person visits on Days 22, 29, and 60 (if this is an in-person visit). Abnormal laboratory test values related to an SAE should continue to be recorded out to Day 60.

Procedure	Screening Visit Day -2 to Day 1	Baseline Visit (Randomization) Day 1	Days 2 through 14 (+/- 1 day)¹	End of Treatment (EOT) Visit or Day 15 (+/- 1 day)²	Post-Treatment Phase Days 16 (+/- 1 day) through Day 29³ (+/- 2 days)	Day 60 (+/- 15 days)	Comments
eGFR)							
Electrocardiogram (ECG)	X						ECG will be collected per protocol at the Screening Visit. If an ECG is collected as SOC within 48 hours of signing Informed Consent, it may be used as the Screening ECG. If ECGs are collected as per SOC on any other days from Day 1 through Day 29 and are clinically significant, these values should be entered into the eCRF on Unscheduled Visit ECG pages.
Physical Measurements	X				X		Screening, Day 22 (+/- 2 days) and Day 29 (+/- 2 days) only. Physical measurements collected within 48 hours of signing Informed Consent may be used as the Screening assessments. Height collected at screening only.
Sequential Organ Failure			X	X	X		This is completed only if the subject is admitted to the ICU. It should only be

Procedure	Screening Visit Day -2 to Day 1	Baseline Visit (Randomization) Day 1	Days 2 through 14 (+/- 1 day)¹	End of Treatment (EOT) Visit or Day 15 (+/- 1 day)²	Post-Treatment Phase Days 16 (+/- 1 day) through Day 29³ (+/- 2 days)	Day 60 (+/- 15 days)	Comments
Assessment (SOFA) ⁴							completed upon ICU admission and at Day 29 if the patient is still in the ICU.

⁴ The Sequential Organ Failure Assessment Score (SOFA) will be completed as a supplemental assessment (not part of a scheduled visit) if the subject is admitted to the ICU during the course of the study. The Glasgow Coma scale is part of the SOFA assessment and should be completed along with the SOFA assessment.

Procedure	Screening Visit Day -2 to Day 1	Baseline Visit (Randomization) Day 1	Days 2 through 14 (+/- 1 day)¹	End of Treatment (EOT) Visit or Day 15 (+/- 1 day)²	Post-Treatment Phase Days 16 (+/- 1 day) through Day 29³ (+/- 2 days)	Day 60 (+/- 15 days)	Comments
National Early Warning Score (NEWS2) assessment	X		X	X	X	X	
NEWS2 assessments collected as per SOC within 48 hours of signing Informed Consent may be used as the Screening assessments. NEWS2 assessments will be collected daily while subject is in the hospital. This assessment may be assessed in the AM or PM but around the same time every collection day within 3 hours and entered on the eCRF. NEWS2 is a collection of ongoing vitals related to: respiration (breaths/min), SpO2 Oxygen saturation (%), BP, pulse, consciousness, temperature to provide a total NEWS2 score. The timing of the NEWS2 for the purpose of the eCRF in the study should also correlate timing with the collection of the SpO2 and FiO2.
 
After hospital discharge, NEWS2 should be collected at in-person visits on Days 22, 29, and 60 (if this is an in-person visit).

Vital Signs	X	X	X	X	X	X	Vital signs collected as per SOC

Procedure	Screening Visit Day -2 to Day 1	Baseline Visit (Randomization) Day 1	Days 2 through 14 (+/- 1 day)¹	End of Treatment (EOT) Visit or Day 15 (+/- 1 day)²	Post-Treatment Phase Days 16 (+/- 1 day) through Day 29³ (+/- 2 days)	Day 60 (+/- 15 days)	Comments
							
within 48 hours of signing Informed Consent may be used as the Screening assessment. While subjects are in the hospital, vital signs will be collected once daily in the AM or PM but around the same time every day within 3 hours and entered on the eCRF.
 
After hospital discharge, vital signs should be collected at in-person visits on Days 22, 29, and 60 (if this is an in-person visit).

SpO2 and FiO2	X	X	X	X	X	X	
SpO2 and FiO2 collected as part of SOC within 48 hours of signing Informed Consent may be used as the Screening assessments. While the subject is in the hospital, this is collected in the eCRF once daily and should correlate (AM or PM) with the time the vital signs and the NEWS2 are collected.
 
After hospital discharge, SpO2 and FiO2 should be collected at any in-person visits on Days 22, 29, and 60 (if this is an in-person visit).

Procedure	Screening Visit Day -2 to Day 1	Baseline Visit (Randomization) Day 1	Days 2 through 14 (+/- 1 day)¹	End of Treatment (EOT) Visit or Day 15 (+/- 1 day)²	Post-Treatment Phase Days 16 (+/- 1 day) through Day 29³ (+/- 2 days)	Day 60 (+/- 15 days)	Comments
Arterial Blood Gas (ABG)							Arterial Blood Gas (ABG) is not a required assessment for the protocol. However, if it is collected as per SOC within 48 hours from signing Informed Consent through Day 29, this data should be entered in the eCRF in Unscheduled Visit ABG pages.
6-point ordinal scale	X	X	X	X	X	X	While in the hospital, this is collected once daily. This may be collected in the AM or PM at the discretion of the Investigator or staff but should be collect around the same time (within 3 hours) every day. If subjects are discharged from the hospital and unable to return for in-person visits, this scale should be assessed by phone on Days 15, 22, and 29. After hospital discharge, this assessment should be collected at in-person visits on Days 22, 29, and 60 (if an in-person visit).

Procedure	Screening Visit Day -2 to Day 1	Baseline Visit (Randomization) Day 1	Days 2 through 14 (+/- 1 day)¹	End of Treatment (EOT) Visit or Day 15 (+/- 1 day)²	Post-Treatment Phase Days 16 (+/- 1 day) through Day 29³ (+/- 2 days)	Day 60 (+/- 15 days)	Comments
Chest x-ray	X			X			Chest x-ray required at screening and End of Treatment or Day 15 (if subject is in the hospital on Day 15). If a chest x-ray is collected within 48 hours of signing Informed Consent, this may be used as the Screening chest x-ray assessment. If a chest x-ray is collected as per SOC after Day 15 until Day 29, these data should be entered into the eCRF on Unscheduled Visit Chest x-ray pages.
Serum antibody test for SARS-CoV2 virus				X	X		The serum antibody test should be done no earlier than Day 15 and before Day 60
CCI							

Procedure	Screening Visit Day -2 to Day 1	Baseline Visit (Randomization) Day 1	Days 2 through 14 (+/- 1 day)¹	End of Treatment (EOT) Visit or Day 15 (+/- 1 day)²	Post-Treatment Phase Days 16 (+/- 1 day) through Day 29³ (+/- 2 days)	Day 60 (+/- 15 days)	Comments
							Screening Visit
Liver function tests (LFTs) (AST, ALT, alkaline phosphatase, and bilirubin -Total, Direct, Indirect)	X			X			LFTs will be collected per protocol at the Screening Visit and on Day 15. If LFTs are collected as per SOC within 48 hours of signing Informed Consent, these may be used as the Screening values. If additional LFTs are collected as per SOC on any other days from Day 1 through 29 and are clinically significant, these values should be entered into the eCRF on Unscheduled Visit LFT pages.
Pregnancy Test for women of childbearing potential (WOCBP)	X			X	X Day 29 only	X	Urine test is recommended, but serum may also be done if preferred by Investigator/Staff. WOCBP must have a negative pregnancy test at the Screening Visit before being randomized and treated with IP. If a WOCBP is discharged from the hospital prior to Day 22, a urine pregnancy test should be collected at in-person visits on Days 22 (+/- 2 days), 29 (+/- 2 days), and 60 (+/- 15 days) (if an in-person visit).

Procedure	Screening Visit Day -2 to Day 1	Baseline Visit (Randomization) Day 1	Days 2 through 14 (+/- 1 day)¹	End of Treatment (EOT) Visit or Day 15 (+/- 1 day)²	Post-Treatment Phase Days 16 (+/- 1 day) through Day 29³ (+/- 2 days)	Day 60 (+/- 15 days)	Comments
Sparse PK sampling			X Day 5 (+/- 2 days)				PK sampling should be obtained on Day 5 (+/- 2 days). PK may include samples collected at Pre-dose, 0.5, 1, 2.5 and 5h (all samples collected within +/-0.5h).
Concomitant Medication Collection	X	X	X	X	X		Concomitant medications are captured from first dose of study drug through Day 29.
Concomitant Procedures Collection	X	X	X	X	X		Concomitant procedures are captured from first dose of study drug through Day 29 except for the start of supplemental oxygen which could start within 48 hours of randomization. This data should be captured on the concomitant procedures page.
AE Assessment		X	X	X	X		Non-serious AEs are captured from first dose of study drug through Day 29. Non-serious adverse events should be followed until conclusion or stabilization or reported as SAEs if they become serious. Follow-up is also required for non-serious AEs that

Procedure	Screening Visit Day -2 to Day 1	Baseline Visit (Randomization) Day 1	Days 2 through 14 (+/- 1 day)¹	End of Treatment (EOT) Visit or Day 15 (+/- 1 day)²	Post-Treatment Phase Days 16 (+/- 1 day) through Day 29³ (+/- 2 days)	Day 60 (+/- 15 days)	Comments
							cause interruption or discontinuation of study drug or those that are present at Day 29. Note: For this study, admission and discharge to the ICU should be captured on the Adverse Event eCRF.
SAE assessment	X	X	X	X	X	X	
SAEs are captured any time after signing consent through the Day 60 visit.
 
All SAEs should be followed until resolution or stabilization.

Administer study drug		X	X				
IP is dispensed every 8 hours (+/- 2 hours) during the Treatment Phase for a total of 42 doses.
 
If subjects are discharged from the hospital to home prior to Day 15 they will be discontinued from study drug but continue in the study. Please note that due to the potential for rebound from withdrawal of an immunomodulating agent, subjects who are planning to be discharged should be off of study drug for at least

Procedure	Screening Visit Day -2 to Day 1	Baseline Visit (Randomization) Day 1	Days 2 through 14 (+/- 1 day) ¹	End of Treatment (EOT) Visit or Day 15 (+/- 1 day) ²	Post-Treatment Phase Days 16 (+/- 1 day) through Day 29 ³ (+/- 2 days)	Day 60 (+/- 15 days)	Comments
							24 hours before release from the hospital. If the subject is discharged to a step-down or satellite care facility where they can be monitored for safety, they should continue receiving study drug until completing 42 doses.
Telephone Visits				X	X	X	If subjects are released from the hospital prior to Day 15, and an EOT visit was conducted, a follow-up phone call should be made on Days 15, 22, and 29 to assess 6-point ordinal scale, AEs/SAEs, and concomitant medications and procedures. If the subject remains in the hospital on Days 15, 22, or 29, telephone visits are not required, but in-person visits should be conducted.

Procedure	Screening Visit Day -2 to Day 1	Baseline Visit (Randomization) Day 1	Days 2 through 14 (+/- 1 day)¹	End of Treatment (EOT) Visit or Day 15 (+/- 1 day)²	Post-Treatment Phase Days 16 (+/- 1 day) through Day 29³ (+/- 2 days)	Day 60 (+/- 15 days)	Comments
Safety Follow-up Visit (Day 60)						X	
If subjects have not had an in-person visit from the time of hospital discharge prior to Day 60, the Day 60 visit should be an in-person visit, and the same assessments that would have been collected on Day 29 should be performed.
 
If subjects have been able to have an in-patient or an in-person visit on Day 29, then the Day 60 visit will be done by telephone to collect 6-point ordinal scale, status of any AEs/SAEs ongoing at time of discharge, any new SAEs, and to confirm subject mortality.

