3.2.2 Other Secondary Endpoints

1. Number of subjects with deaths, SAEs, severe AEs, and Grade 3 or 4 laboratory test abnormalities at any time on study. All AEs are from AE/SAE eCRFs. Grade 3 or 4 laboratory test abnormalities are determined from laboratory test values graded using standardized criteria defined in the SAP (e.g., CTCAE) from laboratory test eCRFs.
2. Number and percentage of subjects with severe or life-threatening bacterial, invasive fungal, or opportunistic infections at any time through Day 29 from AE/SAE eCRFs.

3. Number and percentage of subjects with intranasal administration reactions at any time through Day 29 from AE/SAE eCRFs.
4. Proportion of subjects with 250% reduction in eGFR from baseline at any time on study from laboratory test eCRFs.

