6.3.5 Laboratory Assessments

The investigator must review all laboratory reports, document this review, and record any clinically significant relevant changes occurring during the study in the AE section of the eCRF (see guidance in [Section 8.4.2](#)). The laboratory reports must be filed with the source documents. Clinically significant abnormal laboratory test findings are those which are not associated with the underlying disease, unless judged by the investigator to be more severe than expected for the subject's condition.

All laboratory tests with abnormal values collected through Day 29 considered to be clinically significant by the Investigator should be reported as adverse events and repeated and recorded in the eCRF until the values return to normal or baseline or are no longer considered clinically significant by the investigator or medical monitor. Abnormal laboratory test values related to an SAE should continue to be recorded out to Day 60.

If such values do not return to normal/baseline within a reasonable period of time judged by the investigator, the etiology should be identified, and the sponsor notified.

All protocol-required laboratory assessments must be conducted in accordance with [Table 1](#).

If laboratory values from non-protocol specified laboratory assessments performed as per SOC require a change in subject management or are considered clinically significant by the investigator (e.g., SAE or AE), then the results must be recorded in the eCRF.

6.3.5.1 *Safety Laboratory Testing*

Blood and urine samples will be obtained as outlined in [Table 1](#) for clinical laboratory evaluations. If clinical labs are collected within 48 hours of signing Informed Consent, they may be used as the Screening labs. Laboratory samples will be collected and processed via hospital/site standard operating procedure (SOP).

Clinical Safety Labs:

- **Hematology:** red blood cell (RBC) count, hemoglobin, hematocrit, platelets, white blood cell (WBC) count, and differentials (neutrophils, basophils, eosinophils, lymphocytes, monocytes, bands)
- **HbA1c**
- **Chemistry:** albumin, calcium, creatinine kinase (CK), serum glucose, LDH, total protein, potassium, sodium, uric acid, blood urea nitrogen (BUN), serum creatinine, chloride, and bicarbonate
- **eGFR and method of calculation**

LFTs:

- AST, ALT, alkaline phosphatase, total bilirubin, direct bilirubin, and indirect bilirubin

Urinalysis:

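### Off-schedule routine-care laboratory values that meet two numeric safety endpoints need not be entered in the eCRF, and the entry rules conflict after the Treatment Phase

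*Protocol*

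**What the plan says.** **Endpoints.** Section 3.2.2, endpoint 1, is the "Number of subjects with deaths, SAEs, severe AEs, and Grade 3 or 4 laboratory test abnormalities at any time on study". Its laboratory part is numeric: "Grade 3 or 4 laboratory test abnormalities are determined from laboratory test values graded using standardized criteria defined in the SAP", read from the laboratory eCRFs. Endpoint 4 is the proportion with a "reduction in eGFR from baseline at any time on study from laboratory test eCRFs"; Section 2.2.2 sets the threshold at 50% or more. Neither refers to cause.

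**Entry of off-schedule routine-care results.** The Table 1 row for safety labs, which include eGFR, asks for entry of values "collected as per SOC on any other days and are clinically significant, these values should be entered into the eCRF". The liver-test row applies the same filter for Days 1 to 29, and Section 4.3.6.1 applies it out to Day 29 for subjects still in hospital after treatment. Section 6.3.5 says that results must be recorded if tests "performed as per SOC require a change in subject management or are considered clinically significant by the investigator". The same section describes clinically significant findings as those "which are not associated with the underlying disease, unless judged by the investigator to be more severe than expected" for the subject's condition.

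**Table 1 footnote 3.** For subjects still in hospital or in a recovery facility after the Treatment Phase: "Any clinical safety labs, urinalysis, LFTs, ECGs, or chest x-rays collected as per SOC should be entered into the eCRF in unscheduled visit pages". There is no significance filter.

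**Source.** "The laboratory reports must be filed with the source documents" (Section 6.3.5).

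**The concern.** The endpoints apply a numeric threshold regardless of cause. The entry rule asks whether the investigator thinks the result goes beyond what the disease explains. In patients hospitalized with COVID-19, a marked laboratory abnormality or a renal decline can readily be put down to the disease, so the two tests can give different answers for the same value. The SAP can define grading, but it cannot grade a value that was never entered. At stake are the completeness of two safety counts and their comparability across sites, since one site's expected finding may be another's significant one.

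After treatment there is a second problem. A site with an in-hospital subject cannot tell whether to enter every routine-care lab or only the significant ones.

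**Working it through.** There is no stated figure to reproduce. The check compares the texts and then counts days.

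**1. Can a qualifying value stay out?** Take an off-schedule routine-care value that is Grade 3 or an eGFR at half of baseline, and go through each route to recording:
- Clinically significant (Table 1 rows, 4.3.6.1): not met if judged disease-associated and no worse than expected.
- Change in management (6.3.5): not met if care is unchanged.
- Corrective therapy, or interruption or discontinuation of study drug (8.4.2): not met if none occurs. This route leads to the AE page or SAE form, not the laboratory page.
- SAE-related (Table 1, 6.3.5): not met if there is no SAE. The liver-injury definition in 8.3.5 also requires that no other cause be apparent.
- Scheduled draw: not met if the abnormality is absent on all of them.

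If all of these fail together, none of those rules requires entry. The one remaining route is footnote 3, which applies only after treatment and is contradicted there (step 2).

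**2. Where do the rules conflict?** For in-hospital subjects after the Treatment Phase, footnote 3 requires every routine-care safety lab and liver test, while 4.3.6.1 and the Table 1 rows require only significant ones. Footnote 3 does not reach Days 1–14, where the filter is applied consistently.

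**3. How many days rely on the off-schedule rules?** Inputs from Table 1: safety-lab draws on Days 1, 2, 5, 10, 15, 22 and 29; one liver-test draw after screening, at EOT/Day 15. Assumptions: nominal days, subject in hospital throughout.
- Safety labs: 29 − 7 = 22 days without a draw. Ten are in Days 1–14 and 14 − 2 = 12 are in Days 16–29.
- Liver tests: 29 − 1 = 28 days without a draw.

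An abnormality with onset day s lasting d days misses every draw if none of days s to s + d − 1 is a draw day. The durations are chosen as a range. Onset days, out of 14, that miss every draw:

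| Onset period | Test | d = 1 | d = 3 | d = 5 | d = 7 |
|---|---|---|---|---|---|
| Days 1–14 | Safety labs | 10 | 4 | 0 | 0 |
| Days 1–14 | Liver tests | 14 | 12 | 10 | 8 |
| Days 16–29 | Safety labs | 12 | 8 | 4 | 0 |
| Days 16–29 | Liver tests | 14 | 14 | 14 | 14 |

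For example, a 3-day abnormality in Days 16–29 misses both safety-lab draws for onsets 16–19 and 23–26, which is 8 days. The Days 16–29 rows show exposure only if the filter prevails over footnote 3.

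**4. Does the eGFR discontinuation rule guarantee capture?** Exclusion 2 admits a screening eGFR of 30 mL/min or more. Taking that as baseline, half of 30, 60 and 90 is 15, 30 and 45. Section 6.6 acts below 15. A value from 15 up to half of baseline meets endpoint 4 without reaching that rule, so the rule does not guarantee entry.

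**5. End day.** The liver-test row and 4.3.6.1 stop at Day 29; the endpoints do not. From Day 29 to Day 60 is 60 − 29 = 31 days (16 to 46 with the ±15-day window). If Day 29 was in hospital or in person, Day 60 is a telephone contact with no scheduled labs.

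**The case against.** The strongest defence is that a loss requires a long chain of conditions: off-schedule, judged expected, no change in care, no corrective therapy, no SAE, and absent at every scheduled draw. Scheduled safety labs on seven days carry no filter. Endpoint 4 names the laboratory eCRFs as its source, so it can be read as a count over recorded values. Reports are kept in source, and sites receive eCRF completion instructions (Section 6.1), which are not at hand and may settle the entry rule. All of this limits the likely loss. It does not remove the mismatch: the protocol defines the endpoints by threshold and the entry rule by judgement, and source verification in Section 11.1 is described as checking data already entered.

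A reader might infer more than the text supports on four points:
- *That clinical significance is the only way in.* It is not. The change-in-management route in 6.3.5 stands beside it, and footnote 3 as written admits everything after treatment in hospital or a recovery facility.
- *That the end days contradict each other.* The liver-test row, 4.3.6.1, 6.3.5 and 8.4.2 broadly agree on Day 29, with Day 60 for SAE-related values. The safety-lab row is silent rather than different. What remains is a Day 29 limit against endpoints with no limit.
- *That the day counts measure lost events.* They are days at risk. The Day 15, 22 and 29 windows would shift them, and the other entry routes recover some values.
- *That the treatment comparison is biased.* The study is double-blind and nothing shows that the filter acts differently by arm.

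**Conclusion.** The concern stands as a minor one. As written, the entry filter allows a Grade 3 or 4 value, or an eGFR fall of at least 50%, to be left out when it is off-schedule, judged expected for COVID-19 and without consequence for care. Both counts may therefore be low and partly dependent on site judgement. Liver tests are the most exposed of these blood tests, with one scheduled draw after screening. The conflict between footnote 3 and Section 4.3.6.1 with the Table 1 rows is a definite contradiction, confined to the post-treatment period. The mismatch between Day 29 and the whole study is a lesser point.

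The number of events lost cannot be derived from the protocol. The day counts rest on nominal visit days, continuous hospital stay and assumed durations. Both endpoints are safety counts outside the gatekept testing in Section 9.3.3, so no efficacy conclusion depends on them.

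**What to change.** 1. Reconcile footnote 3 with Section 4.3.6.1 and the Table 1 safety-lab and liver-test rows.
2. Keep the existing triggers (clinically significant, change in management, SAE-related). In addition to them, require entry of every routine-care value that is Grade 3 or higher on the Section 9.3.6 criteria, or an eGFR at or below 50% of baseline, whatever its attributed cause. This must be worded as an addition: a replacement rule would drop lower-grade values that must now be entered.
3. Align the window. Either limit endpoint 4 and the laboratory part of endpoint 1 to Day 29, as endpoints 2 and 3 already are, and say how a Day 29 set deferred to the Day 60 visit (Section 4.3.7) is counted; or extend entry to the end of study. Deaths and SAEs keep their present window.
4. Enter qualifying values already filed in source before database lock.
5. In Section 9.3.6, call these Grade 3–4 laboratory abnormalities and keep the term clinically significant for AE reporting.

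Cost: screening routine-care results against the numeric limits and each subject's baseline eGFR, plus a one-off source review for about 120 subjects. No extra draws or visits are needed. The counts will still depend partly on how often each site draws blood.
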